**Section C: Background Information**

Autism spectrum disorder (ASD) affects as many as 1 out of 59 individuals, with many higher-functioning youth not diagnosed until school-age or later. This equates to ~102,000 children under the age of 14 years in the state of Texas alone. Significant impairment in social and adaptive functioning are common, as are comorbid behavioral health disorders, with anxiety disorders affecting between 50-80% of youth with ASD. Given the relative frequency of anxiety disorders among children with ASD, the associated impairment, and worsening trajectory over time without intervention, there is a great need for treatment that specifically addresses anxiety-related symptoms in ASD.

Cognitive behavioral therapy (CBT) has demonstrated efficacy in a number of studies. However, existing treatment

protocols are delivered by therapists as ‘full-packages’ (i.e., 12-16 clinic sessions), which can be therapist-intensive, costly, impractical for families, and not responsive to parental preferences. Alternative approaches, such as parent-led, stepped-care models that improve accessibility, are efficient, provide personalized care, and lower mental health treatment cost, are greatly needed. Stepped-care models provide a lower-intensity first step (e.g., parent-led, less costly, and more convenient for parents) as the initial treatment with the assumption that a proportion of individuals will respond to the first step and others will need to step up to more intensive treatment. Matching treatment to families’ needs and tailoring subsequent treatment may be an efficient and effective approach, as well as consistent with parents’ desire to help their child. Given this, together with the substantial impairment associated with clinical anxiety in individuals with ASD across the age span, this study proposes to implement a parent-led, flexible, individually-tailored cognitive-behavioral intervention for children with ASD and anxiety.

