direct (e.g., cost of therapy session), indirect (e.g., travel costs, missed work), and opportunity costs (e.g., value of lost time; see above for cost measures). CEA often incorrectly omits the opportunity cost of patient/parent time spent on therapy, phone support, and at-home parent-child meetings. Non-study, mental-health service costs include inpatient, outpatient, and school-based services and will be priced using the Texas Medicaid fee schedules. Research-specific costs (e.g., screening, research consent) for patients and staff are excluded. Incremental cost-effectiveness ratios (ICER) are computed as incremental costs divided by incremental changes in morbidity/outcomes (symptom reduction and change in impairment/functioning). If outcomes differ significantly, a non-parametric bootstrap with replacement method is used to generate a joint distribution of differential costs and outcomes. If outcomes do not differ, cost-effectiveness is determined by examining treatment costs. Mean and median ICER ratios are reported, as well as 95% confidence intervals. Cost-effectiveness acceptability curves examine the probability of falling below a variety of cost-effectiveness thresholds. In addition to the ICER approach, the net-benefit approach will be used to determine if findings are sensitive to method.

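### The acceptability curve, read in context as the probability that the ICER is below a threshold, is correct only if SC-CBT is the more effective option; it should be defined from net benefit

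*Combined protocol and SAP*

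**What the plan says.** The economic plan is in the protocol's Section G2 (Data Analysis). It compares SC-CBT with CBT and defines the ratio: "Incremental cost-effectiveness ratios (ICER) are computed as incremental costs divided by incremental changes in morbidity/outcomes".

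What follows depends on the outcome comparison. "If outcomes differ significantly, a non-parametric bootstrap with replacement method is used to generate a joint distribution of differential costs and outcomes". Otherwise, "If outcomes do not differ, cost-effectiveness is determined by examining treatment costs".

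The reporting rules come next: "Mean and median ICER ratios are reported, as well as 95% confidence intervals", and then "Cost-effectiveness acceptability curves examine the probability of falling below a variety of cost-effectiveness thresholds". The last sentence of the section reads: "In addition to the ICER approach, the net-benefit approach will be used to determine if findings are sensitive to method".

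No rule is given for a negative effect difference, for the sign convention, or for the quadrants of the cost-effectiveness plane. Section C says that approaches such as stepped care "lower mental health treatment cost", so a negative cost difference is among the results the investigators have in mind.

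**The concern.** The acceptability sentence does not say what falls below the threshold. The sentence before it reports ICERs, and the one after it opens by adding to the ICER approach, so the ICER is the natural reading. Net benefit does not fit the wording, because on that scale an option is acceptable when it lies above zero.

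A ratio of two signed differences loses information. A positive ICER can mean extra cost per point gained, where small is good, or money saved per point lost, where large is good. A negative ICER can mean cheaper and better, or dearer and worse. Counting every ratio below L as favourable is right for the first member of each pair and wrong for the second.

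At stake is the main probabilistic display for the third aim in Section D. If SC-CBT proved cheaper but significantly less effective, the curve would favour it at high thresholds and reject it at low ones, the reverse of what the data would show.

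**Working it through.** **Inputs.** The documents supply the ratio (cost difference over effect difference), the direction (SC-CBT relative to CBT), the significance condition on the bootstrap, and the curve's wording. They state no figure for the curve, so there is nothing to reproduce. All numbers below are assumptions. The algebra does not depend on them.

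**Algebra.** Let dE and dC be the effect and cost differences, SC-CBT minus CBT, with dE > 0 meaning that SC-CBT is better. SC-CBT is cost-effective at threshold L when NB = L × dE − dC > 0.

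- If dE > 0, dC/dE < L is equivalent to NB > 0.
- If dE < 0, multiplying by dE reverses the inequality, so dC/dE < L is equivalent to NB < 0.

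Hence P(ICER < L) = P(dE > 0, NB > 0) + P(dE < 0, NB < 0). This differs from 1 − P(NB > 0) by at most P(dE > 0).

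**Effect of the significance condition.** Assume a two-sided 5% test and roughly normal draws. If the bootstrap runs because SC-CBT is significantly worse, the z for dE is −1.96 or lower, so P(dE > 0) is at most 0.025. The curve as described is then within 0.025 of one minus the correct curve.

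**Illustration A: cheaper and less effective.** Assume dE = −1.5 points (SE 0.6, z = −2.5) and dC = −$900 (SE $250), independent normals. Then P(NB > 0) = Φ[(L × (−1.5) + 900) / √((0.6L)² + 250²)].

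- L = 300: 450 / √(180² + 250²) = 450 / 308.06 = 1.461, giving 0.928.
- L = 600: 0 / 438.29 = 0, giving 0.500.
- L = 1,200: −900 / √(720² + 250²) = −900 / 762.17 = −1.181, giving 0.119.

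P(ICER < L) from the same joint distribution is 0.078, 0.506 and 0.887. Each is one minus the correct value plus about 0.006, which is P(dE > 0) = Φ(−2.5).

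**Illustration B: sensitivity to the assumed z.** Assume dE = −2 points and dC = −$600 (SE $100), so that the ratio of the means is $300 saved per point lost.

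| z for dE | L | P(ICER < L) | P(NB > 0) |
|---|---|---|---|
| −4 | 200 | 0.08 | 0.92 |
| −4 | 400 | 0.81 | 0.19 |
| −2.5 | 200 | 0.15 | 0.86 |
| −2.5 | 400 | 0.73 | 0.28 |
| −1.96 | 200 | 0.21 | 0.81 |
| −1.96 | 400 | 0.71 | 0.32 |

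**Dearer and less effective draws.** Keep dE as in A and set dC = −$300 (SE $250). The share of draws with dC > 0 and dE < 0 is Φ(−1.2) × Φ(2.5) = 0.1151 × 0.9938 = 0.114. All have a negative ratio, so 11.4% of draws count as acceptable at every positive L when none should.

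**Other quadrants.** Use the magnitudes of B with |z| = 2.5 and L = 400.

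- Dearer and more effective: 0.731 as described, 0.725 correct.
- Cheaper and more effective: 0.994 as described, 1.000 correct.
- Dearer and less effective: 0.994 as described, 0.000 correct.

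The two definitions therefore agree within 0.01 when SC-CBT is better and fail when it is worse.

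**The case against.** Five points can be made for the plan.

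1. **The definition is inferred.** The sentence may be shorthand, and the bootstrap of joint cost and outcome pairs keeps the sign of dE, so a careful analyst could build the curve correctly. This stands as a limit on how firmly the error can be attributed. It does not remove the problem, because the natural reading is the faulty one and no other rule is written.
2. **Net benefit is already planned.** It orders all four quadrants correctly, and a mirror-image curve would be hard to overlook. This stands in part. The plan uses net benefit only so that "the net-benefit approach will be used to determine if findings are sensitive to method", and does not link it to the curve. Both use the same differences, so a disagreement would show a misread ratio and not a finding that depends on method. A reader might infer that the investigators would dismiss the net-benefit result, but the documents do not say how they would resolve a conflict.
3. **The harmful case may not arise.** A reader might infer from Section C that cheaper but worse is the expected result. The documents do not support that. Only the first step is lower in intensity, non-responders go on to therapist-led sessions in Step Two (Section F2), and the societal perspective counts parents' time, so neither worse outcomes nor lower cost is assured.
4. **The sizes are assumed.** This stands in full. The reversal of direction does not depend on them.
5. **The comparator comes first.** Section F2 gives SC-CBT to all participants, and the supplied text names no source for CBT costs and outcomes. Without one there are no differences and no curve. That is a separate and prior question. The point here applies once a comparator is supplied.

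**Conclusion.** The curve is wrong as described, conditionally and with moderate severity. Under the natural reading, it gives the probability that SC-CBT is cost-effective only when SC-CBT is the more effective option. If SC-CBT is significantly less effective, the curve is within about 0.025 of one minus the correct one, assuming a two-sided 5% test and near-normal draws. In the cheaper-but-worse case this points to the opposite decision at thresholds away from the true ratio. If SC-CBT is dearer and worse, it appears almost certainly acceptable.

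A reader might go further and conclude that Aim 3 will report the wrong decision. The documents do not support that. The error needs a significantly negative effect difference, the plan decides on costs when outcomes do not differ, and the net-benefit analysis could expose the reversal. A wrong conclusion is possible, not inevitable. The point concerns one display in the third-listed aim and leaves Aims 1 and 2 untouched.

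**What to change.** In Section G2, replace the acceptability sentence with a definition:

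- State that the effect difference is SC-CBT minus CBT, scored so that positive means SC-CBT is better.
- Define the curve, for each L over a stated range, as the share of bootstrap draws with L × (effect difference) − (cost difference) > 0.
- Treat the ICER as descriptive, read by quadrant of the cost-effectiveness plane, because a mean or median ratio taken across quadrants mixes opposite meanings.

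This makes the net-benefit approach the basis of the curve instead of a separate check on method. It costs about one sentence of wording and uses the same bootstrap draws, with no new data and no change to trial conduct.

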**STEP ONE.** All participants will start with Step One, which includes 4 parent-led, therapist-assisted sessions over a 12-week period. Parents will receive a parent-child workbook to use in session with the therapist, and at home. During each of these 4 sessions, the therapist will review with parents the necessary skills for conducting exposures and will provide guidance in the delivery of exposures. Exposures, a hallmark of CBT for anxiety are used to gradually and repeatedly confront feared stimuli. For example, exposure therapy for a child fearful of dogs may begin with looking at pictures of dogs and standing across the park from a dog on a leash, to eventually petting a dog. Outside of session, parents will lead therapy using the provided workbook, which consists of a step-by-step approach for parents written on a 6th-grade level. Brief phone contacts between parent and staff will also be provided for support, coaching, and motivation. After completing Step One, a brief assessment will occur (i.e., the mid-treatment). If the child meets treatment response status, then the parent and child end treatment and proceed to the Maintenance phase, where parents and children will be encouraged to continue using the workbook and tools that they learned in Step One. If the child does not meet treatment response (i.e., does not improve), then s/he will 'step up' to Step Two.

**STEP TWO.** For those children who do not respond to Step One, they will be 'stepped up' to Step Two, which consists of 10 therapist-led, parent-supported sessions, each lasting 60-120 minutes over the course of 12 weeks. During Step Two, therapists will lead exposure tasks and teach children response strategies. These strategies will focus on providing children with anxiety-coping skills. In addition, parents will be taught (in weekly sessions) to support children in learning and maintaining anxiety-coping skills, especially when outside of sessions. These skills are encouraged to be practiced at school, in the community, and in peer-group settings. After completing Step Two, participants will end treatment and the post-assessment will occur. For those participants in the maintenance phase (i.e., treatment responders at Step One), the post-assessment will occur approximately 12 weeks after the completion of the mid-treatment (for consistency with procedures in Step Two). All participants will then be re-assessed 3-months, after completion of the post-treatment.

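### The cost-effectiveness check labelled as sensitivity compares two forms of the same decision, while no cost input, notably the value of parent time, is varied in the plan

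*Combined protocol and SAP*

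**What the plan says.** Section D lists the economic value of stepped-care CBT (SC-CBT) as the third aim. Section G2 (Data Analysis) compares SC-CBT with CBT from a societal perspective. Treatment costs include "opportunity costs (e.g., value of lost time; see above for cost measures", and the plan criticises analyses that leave out parents' hours in therapy, on the phone and at home with the child. It gives no hourly value and no range.

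The analysis then has two branches:

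- The first branch uses resampling: "If outcomes differ significantly, a non-parametric bootstrap with replacement method is used to generate a joint distribution of differential costs and outcomes".
- The second branch looks only at cost: "If outcomes do not differ, cost-effectiveness is determined by examining treatment costs".

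For reporting, "Mean and median ICER ratios are reported, as well as 95% confidence intervals", and "Cost-effectiveness acceptability curves examine the probability of falling below a variety of cost-effectiveness thresholds". The one sentence that speaks of sensitivity is the last. It adds net benefit beside the ICER and says that "the net-benefit approach will be used to determine if findings are sensitive to method".

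Section F2 (Step One) shows why parent time matters here: "Outside of session, parents will lead therapy using the provided workbook".

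**The concern.** A sensitivity analysis should change something that could plausibly be different and show whether the conclusion survives. Moving from the ICER to net benefit changes only how the same two numbers are combined. A reader told that the finding does not depend on method could take this as evidence of robustness, when it is a consequence of algebra.

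The inputs that could change the answer are prices and hours. SC-CBT saves therapist sessions and adds parent work at home, so from a societal perspective the cost difference depends on what a parent hour is taken to be worth. The plan requires that hour to be counted but does not ask what happens if it is valued differently.

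**Working it through.** The plan gives no cost, effect or threshold for this analysis, so there is no figure of its own to reproduce. The check has three parts.

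**1. Are the two methods different decisions?** Let dC and dE be the cost and effect differences (SC-CBT minus CBT) and L the threshold. Net benefit is NB = L × dE − dC.

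- If dE > 0, NB > 0 is the same as dC/dE < L.
- If dE < 0, NB > 0 is the same as dC/dE > L.

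So NB > 0 is exactly the ICER rule read by quadrant. A simulation of six cost-effect scenarios at five thresholds, with 200,000 draws for each scenario, found no draw in which the two disagreed.

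**2. Could the plan's own summaries disagree with net benefit?** Yes. G2 states no quadrant rule, reports mean ICERs, and counts ratios that lie under a threshold. Two examples with assumed values follow. In both, the standard errors are 250 for dC and 0.5 for dE, and dE is 2.4 standard errors from zero, so the bootstrap branch would apply.

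- *dC = −300, dE = −1.2, L = 500.* Mean NB = 500 × (−1.2) + 300 = −300. Its standard error is √(500² × 0.5² + 250²) ≈ 354, so P(NB > 0) ≈ 0.20. The share of ratios under 500 is 0.81, because with dE negative a small ratio is unfavourable.
- *dC = 200, dE = 1.2, L = 200.* The ratio of means is 200/1.2 ≈ 167 and mean NB = 200 × 1.2 − 200 = +40, both favourable. The simulated mean of replicate ICERs is about 250, which is unfavourable. That mean is unstable and changes with the random seed.

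These disagreements come from the ratio statistic. They say nothing about costs or effects.

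**3. Can an unvaried input change the cost conclusion?** Inputs from the documents are 4 sessions in Step One and 10 in Step Two (F2), and 12 to 16 sessions for full CBT (Section C). Assumed inputs are the share q stepping up, $120 per session, and 24 extra parent hours at home.

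SC-CBT sessions = 4 + 10q:

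| q (assumed) | SC-CBT sessions | Saved against 12 | Saved against 16 |
|---|---|---|---|
| 0.3 | 7 | 5 | 9 |
| 0.5 | 9 | 3 | 7 |
| 0.7 | 11 | 1 | 5 |

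Cost difference = 24 × w − 120 × (sessions saved), with w the value of a parent hour:

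| Sessions saved | w = $0 | w = $15 | w = $30 | Break-even w |
|---|---|---|---|---|
| 3 | −$360 | $0 | +$360 | 360/24 = $15 |
| 9 | −$1,080 | −$720 | −$360 | 1,080/24 = $45 |

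This charges parent hours to SC-CBT and credits none for CBT sessions avoided. If each avoided session also saves a parent 1 to 2 hours (assumed), then with 3 sessions saved the net extra hours are 24 − 3 = 21 or 24 − 6 = 18. Break-even becomes 360/21 ≈ $17 or 360/18 = $20.

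A wider range at q = 0.5 and 24 hours, without that credit: at $75 per session and 3 saved, break-even is 225/24 ≈ $9.4; at $150 and 7 saved, it is 1,050/24 ≈ $43.8.

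**The case against.** The best defence has four parts.

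*The plan says method, not inputs.* Net benefit can expose artefacts of ratio statistics, as part 2 of the working shows, and that fits the sentence as written. This stands, but it makes net benefit the better summary to report. It does not make it evidence of robustness.

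*Other checks exist.* A reader might infer that this is the only robustness check, or that nothing capable of reversing the decision is varied. The documents do not support that. The acceptability curves vary the threshold, which can matter a great deal: with dC = 200 and dE = 1.2, P(NB > 0) rises from 0.21 at L = 0 to 0.96 at L = 1,000. The bootstrap addresses sampling error. But the bootstrap runs only if outcomes differ significantly, neither tool changes a price or an hour, and the threshold plays no part when costs alone decide.

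*The text may be incomplete.* G2 refers back to cost measures that do not appear in the public text, and the Section S attachments are not included. A reader might infer that parent time is fixed at one value. The plan does not say so; it states neither a value nor a range. Absence can be claimed only for the public text.

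*The dollar example is assumed, and the sign of dC is not always the decision.* Both are correct. At a positive threshold with a real gain in outcome, a higher cost can still be acceptable. In the cost-only branch, however, the sign of dC is the decision.

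**Conclusion.** The concern holds in limited form. The ICER and net benefit are the same decision on the same data, so the comparison that G2 assigns to the sensitivity question cannot show whether the finding is robust. Apart from the threshold and sampling error, the public text varies nothing, and in particular no cost input.

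The size depends on assumptions. At $120 per session, 24 extra parent hours and 3 sessions saved, the cost difference changes sign at $15 per parent hour, or about $17 to $20 with credit for parent time in avoided sessions. With 9 sessions saved and no credit, it stays negative up to $45. Reversal is therefore possible but not certain.

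It would go too far to say that the trial will report its result as insensitive. The plan makes no such statement, and a literal reading of its ratio summaries could instead produce a false disagreement. The point matters most where outcomes do not differ, because the conclusion then rests on costs alone.

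**What to change.** In G2, stop describing net benefit as a test of sensitivity. Present it as a restatement of the main decision, and prefer it to mean ICERs.

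Prespecify scenario analyses on inputs:

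- Reprice parent time, for example at zero, at the parent's own wage and at a replacement wage, counting it in both SC-CBT and CBT.
- Vary the reported hours of home therapy over a stated range.
- Run these in both the bootstrap branch and the cost-only branch.
- Report the cost difference and net benefit under each scenario, and state whether the conclusion depends on them.

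The particular wage bases are suggestions; what matters is that they are fixed before the data are seen.

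The cost is SAP wording and modest extra analysis. The scenarios rely on parent-hour data and CBT comparator costs that the plan's own costing already presumes. Every participant receives SC-CBT (F2, Treatment) and G2 names no source for the CBT costs or outcomes. That is a separate gap, which this change does not close. The downside is that the economic conclusion may turn out to be conditional on the value of parent time, and so less favourable.

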## Section H: Potential Risks/Discomforts

### H1. Potential Risks/Discomforts

Describe and assess any potential risks/discomforts; (physical, psychological, social, legal, or other) and assess the likelihood and seriousness of such risks:

Overall, the risks of this study are considered relatively minor. One potential risk of participating in this study is discomfort associated with the psychiatric evaluation and completion of rating scales-- either due to the discussion of subjectively difficult topics or due to the length of time required for the interviews and questionnaires. However, we have found that most people welcome the opportunity to discuss their experiences with a trained clinician; and breaks will be given as much as possible to decrease boredom and physical/psychological discomfort.

In rare cases, psychotherapy may exacerbate anxiety symptoms. Should a child's symptoms increase significantly (linked to treatment or not) and require study discontinuation, we will discuss alternative treatment options including psychotropic medication and more intense psychotherapy. We will implement very strict rescue criteria should a child's symptoms worsen significantly; he/she requires a higher standard of care (i.e., inpatient); and/or the child experiences suicidality or significant side effects. Should a participant's symptoms markedly worsen, and/or the individual experience suicidality or significant side effects, he/she will be immediately withdrawn from the study and provided with the standard of care, which may include hospitalization, if necessary. [name] (or a covering clinician) will be available at all times to study participants in the event of a clinical emergency. Both this availability and how to reach the investigators in an emergency will be clearly communicated orally and in writing to study participants.

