#### ASSESSMENTS

All participants will be asked to cooperate in assessments that will occur as described above. All assessments will be conducted with an independent evaluator (IE). The IE will be an experienced clinician, trained professional, or advanced graduate trainee (supervised by a clinician). The measures that will be administered will include both IE-rated and participant-rated scales (please see attachment in section S). To reduce burden for families, post-assessment and 3-month follow-up measures will be completed through a secure connection using video-conferencing software (Zoom). Zoom is a secure HIPAA-compliant video-conferencing software.

In addition to completing rating scales, participants will be asked to participate in several objective assessment tasks, examining physiological and motor characteristics. These tasks will be given at baseline and at post-treatment, and will measure the participants gait performance (e.g., gait speed) and balance (e.g., center of mass sway). Both gait performance and balance will be assessed on-site during the in-person visits through the use of wearable sensors. Sensors transmit data to a BCM encrypted laptop via Bluetooth function (wireless), and data are saved in the laptop automatically. The sensor data will not include identifiable information such as name and date of birth. We will use HIPAA compliant BCM Box for transmitting the collected data and for storage. Data collected for each participant will be coded to ensure confidentiality. Only study personnel will have access to subjects' records. Data may also be shared with study's co-investigators (on this IRB protocol) through BCM Box. However, data that could in any way identify subjects will not be made public or shared. All of the outcomes in these tasks will be measured using previously validated wearable sensors (more information attached in section S).

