### Section G: Sample Size/Data Analysis

#### G1. Sample Size

How many subjects (or specimens, or charts) will be used in this study?

Local: 200      Worldwide: 200

Please indicate why you chose the sample size proposed:

We will enroll a total of 200 participants, which achieves sufficient power for the primary and secondary aims. Although we expect slight attrition, the below-mentioned analyses allow for attrition without the loss of data. While MLM does not provide for specific power analyses, the suggested power rules range from 20 participants per group, per level. As such, to be conservative with our power estimates, we aim to enroll 200 participants to ensure we are sufficiently powered for our analyses, accounting conservatively for attrition (~7% at Step One; ~15% at Step Two).

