#### G2. Data Analysis

Provide a description of your plan for data analysis. State the types of comparisons you plan (e.g. comparison of means, comparison of proportions, regressions, analysis of variance). Which is the PRIMARY comparison/analysis? How will the analyses proposed relate to the primary purposes of your study?

Data analysis will involve Multilevel Modeling (MLM) because of the *nesting* nature of the variables. More specifically, because the measures are repeated, the measures are considered the first level of the hierarchy, the individual children are considered the second level, and the treatment groups are considered the third level. A major advantage of MLM is its ability to handle missing data. While more traditional analyses use listwise deletion if a single time point is missing, MLM uses parameter estimates to maximize the use of existing data. Furthermore, the present study will implement a regression discontinuity analysis, which is an application of mixed models within MLM. This will allow us to examine the impact of treatment, without the use of random assignment, as this method allows for the use of groups that are similar at baseline, but then are designated by a predetermined selection cut point.

After assessing responder status and determining which participants receive Step Two treatment and which participants move to the maintenance phase, binary logistic regression will be utilized in an attempt to determine if there are factors significantly predicting group membership. Possible predictors include variables such as age, anxiety severity, internalizing/externalizing problems, and parent characteristics.

Cost-effectiveness analysis examines the relative value of SC-CBT (relative to CBT). CEA is performed from a societal perspective, meaning the costs to the healthcare system and the patient/parents are included. Treatment costs include

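### The rescue rule ends study participation, not only study treatment, and no text shown provides for outcome or cost data afterwards

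*Combined protocol and SAP*

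**What the plan says.** Section H1 sets the rescue rule. Its triggers are marked worsening, significant side effects and suicidality, and the stated consequence is this: "he/she will be immediately withdrawn from the study and provided with the standard of care, which may include hospitalization, if necessary". Just before that, it speaks of a case where a child's "symptoms increase significantly (linked to treatment or not) and require study discontinuation". Neither sentence separates stopping study treatment from stopping study assessments.

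Sections F1 and F2 have all participants assessed at baseline, mid-treatment, post-treatment and 3 months after post-treatment. They do not say whether this includes a child already withdrawn. Section L mentions those who withdraw only to say that assessments they do not complete are unpaid.

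On missing data, Section G1 says "the below-mentioned analyses allow for attrition without the loss of data", and Section G2 adds "A major advantage of MLM is its ability to handle missing data". The logistic regression for aim 2 comes "After assessing responder status and determining which participants receive Step Two treatment and which participants move to the maintenance phase". For aim 3, Section G2 says "Non-study, mental-health service costs include inpatient, outpatient, and school-based services".

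The data and safety monitoring plan and the list of measures are Section S attachments, which are not shown.

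**The concern.** The trigger for withdrawal is closely tied to the outcome being measured. Scores are taken at only four time points, so worsening between visits can end participation before it is scored. Worsening found at a visit would be scored.

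The three aims are exposed differently:

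- **Aim 1 (symptom change).** A multilevel model predicts a child's missing later scores from that child's earlier scores and the group means. If the worsening was never scored, the model predicts improvement for a child who got worse.
- **Aim 2 (predictors of Step One response).** Responder status is set at mid-treatment. A child stopped before then has none, enters neither maintenance nor Step Two, and has no outcome in the logistic regression. No coding rule is given.
- **Aim 3 (cost-effectiveness).** Inpatient care is a named cost item, and the rescue rule ends participation at the point where an inpatient stay may begin. Such costs could go unrecorded in the children most likely to incur them.

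**Working it through.** The plan gives no withdrawal rate, so there is no figure of its own to reproduce. Section H1 calls exacerbation rare. I take rare as 1–3% (assumed): 0.01 × 200 = 2 children and 0.03 × 200 = 6 children.

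**Mean symptom change at post-treatment.** Let p be the share withdrawn. Let w be the withdrawn child's worsening from baseline, as a share of the mean improvement among the children who stay (negative means improvement). Let g be the improvement the model predicts for that child, on the same scale.

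Overstatement = p × (g + w)

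To get g, assume a random-intercept model with time as a factor, correlation 0.5 between visits, a typical mid-treatment improvement of 0.6, and a baseline score at the group mean. With k earlier scores, the child's predicted deviation is k × 0.5 / (1 + (k − 1) × 0.5) times the mean residual.

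- Baseline only: the residual is 0, so g = 1.
- Mid-treatment score shows no change: the residuals are 0 and 0.6, mean 0.3. The weight is 1/1.5 = 0.667, the deviation is 0.2, and g = 0.8.
- Mid-treatment score shows the worsening: for w = 1 the residuals are 0 and 1.6, mean 0.8, deviation 0.533, g = 0.467. For w = 0.5 they are 0 and 1.1, mean 0.55, deviation 0.367, g = 0.633.

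Overstatement with 2 / 6 children withdrawn:

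| Scores before withdrawal | w = 1 | w = 0.5 | w = 0 | w = −0.5 | Zero at |
|---|---|---|---|---|---|
| Baseline only | 2.0 / 6.0% | 1.5 / 4.5% | 1.0 / 3.0% | 0.5 / 1.5% | w = −1 |
| Mid-treatment, no change | 1.8 / 5.4% | 1.3 / 3.9% | 0.8 / 2.4% | 0.3 / 0.9% | w = −0.8 |
| Mid-treatment, worsening scored | 1.5 / 4.4% | 1.1 / 3.4% | – | – | – |

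Simulating the same model (200 children, four visits, REML, 600 runs) gave these values to within 0.1 point. Giving a Step Two group of 100 its own time means, with a mid-treatment score recorded, gave 0.3–5.3%.

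Below the zero point the sign reverses. With baseline only and w = −1.5, the result is 0.01 × (1 − 1.5) = −0.5% for 2 children and −1.5% for 6.

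For scale, if the mean change equals 1 SD of change, the 95% confidence interval half-width is 1.96/√200 = 0.139, about 14% of the effect.

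**Step One response rate.** Suppose 100 of 200 children respond and the stopped children are non-responders who are left out. Then 100/198 − 0.50 = 0.5 points too high, and 100/194 − 0.50 = 1.5 points. At 40% response with 2 left out the excess is 80/198 − 0.40 = 0.4 points; at 60% with 6 left out it is 120/194 − 0.60 = 1.9 points.

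**Cost.** Each unrecorded stay lowers mean stepped-care cost per child by its price divided by 200. At assumed prices this is $5,000/200 = $25 to $10,000/200 = $50. The number of stays and the comparator's costs are not given, so no total follows.

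**The case against.** The strongest objection is that this rests on an absence. The safety plan and the measures sit in attachments that cannot be read here, and handling after withdrawal could well be there. That stands: a reader might infer that the full plan omits follow-up, and the documents cannot show that. It does not remove the point, because H1 states a rule, and following it as written ends participation. The mention of all participants in F1 and F2 does not settle the matter either, since no text applies it to a withdrawn child.

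Three other inferences are tempting and go too far:

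- *The bias always favours stepped care.* It does not. H1 offers medication, more intense psychotherapy or hospitalization, and a child who recovers past the zero points above biases the result the other way.
- *Aim 2 predictor effects are biased.* This is not shown. In logistic regression, missingness that depends only on the outcome shifts the intercept and leaves the odds ratios alone. Bias needs stopped children to differ from other non-responders on the predictors, and the documents do not address that.
- *G1 claims immunity to informative dropout.* Read with G2, its sentence contrasts the model with listwise deletion and says that incomplete cases are kept. It is not plainly a claim of unbiasedness.

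It is also fair to say that the planned Step One attrition of about 7%, or 14 of 200, leaves other children without responder status too. A rule for safety cases does not close that wider gap. Finally, scores taken after rescue care partly reflect that care, so how to use them is a choice of estimand. That is a reason to state the choice, not to leave the data uncollected.

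**Conclusion.** The point holds in a limited form. The written rule ends participation for reasons related to the outcome, and no text shown provides for outcome or cost data afterwards.

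- **Aim 1:** probably small if such cases are rare, about 0.3–6% of the effect at an assumed 1–3% withdrawn. The top of the range needs six children with no mid-treatment score and persistent worsening equal to the full mean improvement. The likely direction favours stepped care, but it is not certain.
- **Aim 2:** the observed response rate is slightly too high, by 0.5–1.5 points at 50% response, if stopped children are left out. Nothing is shown about predictor effects.
- **Aim 3:** the clearest exposure, because the cost plan and the rescue rule pull against each other within the same document. Its size cannot be derived.

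Every rate, price and correlation used here is assumed. A provision in Section S for follow-up after withdrawal would reduce the point to a missing cross-reference.

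**What to change.** In H1, replace withdrawal from the study with stopping study treatment and giving the standard of care. Then:

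1. With the family's agreement, continue the remaining scheduled assessments and the service-use and cost measures. If Section S already provides for this, cross-refer to it in H1.
2. Report the number of children stopped, by step and by trigger.
3. In G2, add a sensitivity analysis that counts children stopped during Step One as non-responders in the logistic regression, without requiring step-up.
4. In G2, add a sensitivity analysis for stopped children with no later score. Assign the baseline score, then baseline worsened by half, then by all, of the mean improvement.

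The cost is a wording change in H1 and G2 and up to three further assessments per affected child. Payments are at most 3 × $40 = $120 per child, or $240–$720 for 2–6 children, plus evaluator time. The route largely exists already: "post-assessment and 3-month follow-up measures will be completed through a secure connection using video-conferencing software".

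The report should state three downsides. Some families in crisis will decline, so some data stay missing. Later scores and costs will partly reflect rescue care. Because H1 covers worsening whether or not treatment caused it, non-responder coding may misclassify some children.
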